6.0 MEASUREMENT OF EFFECT

Because this R34 is a planning grant to prepare for an RCT, we will conduct surveys that collect the same information we would collect in an RCT. Questions reflect the information needed to test the primary and secondary outcomes as well as mediation and moderation models. We will measure the time it takes to conduct each survey and assess participant comfort with responding. Table 2 lists items we will ask about in the survey.

Table 2: Measures and scales used in PartnerCHESS study

Measure	Who	Source	Reference	# Questions	Time (month)
Primary outcomes					
Risky drinking days	Patient	TLFB every 60 days (PhenX)	Collins et al. ⁷⁵	1	0, 2, 4, 6
Days of abstinence	Patient	TLFB every 60 days (PhenX)	Collins et al. ⁷⁵	1	0, 2, 4, 6
Secondary outcomes					
Treatment retention	Patient	Clinic records		0	0, 2, 4, 6
Negative affect	Patient & partner	PANAS	Crawford ⁶⁰	10	0, 2, 4, 6
Depression	Patient & partner	PHQ-8		8	0, 2, 4, 6
Sleep quality	Patient & partner	Smartphone data	Sleep Cycle ⁷⁶	0	0, 2, 4, 6
Exploratory outcomes					
Days of other drug use	Patient & partner	TLFB every 60 days (PhenX)	Collins et al. ⁷⁵	2	0, 2, 4, 6
Health service use	Patient & partner	TLFB every 60 days (PhenX)	McCollister, et al. ⁷⁷	8	0, 2, 4, 6
Risky drinking days	Patient & partner	TLFB every 60 days (PhenX)	Collins et al. ⁷⁵	2	0, 2, 4, 6
Physical/psychological abuse	Patient & partner	Rev. Conflict Tactics Scale	Straus et al. ⁷⁸	8	0, 2, 4, 6
Satisfaction with technology	Patient & partner	Technology Acceptance Model ⁷⁹	Szajna ⁸⁰	10	0, 2, 4, 6
Mediators					
Intrinsic motivation	Partner	Brief Self Control Scale.	Tangney ⁸¹	12	0, 2, 4, 6
Intrinsic motivation	Patient	Commitment to sobriety scale	Kelly ⁸²	5	0, 2, 4, 6
Competence	Patient & partner	CCQ and # of skills used.	Schroder ⁸³	9	0, 2, 4, 6
Relatedness	Patient & partner	Bonding	Kim ⁸⁴	5	0, 2, 4, 6
Moderators					
Gender/Sex	Patient & partner	Question (PhenX tier 1)	Collins et al. ⁷⁵	1	0
PartnerCHESS use	Patient & partner	Smartphone data	McTavish ⁸⁵	0	0, 2, 4, 6
A-CHESS use	Patient	Smartphone data	McTavish ⁸⁵	0	0, 2, 4, 6
Covariates					
Age	Patient & partner			1	0
Education	Patient & partner			1	0

Race/ethnicity	Patient & partner			2	0
Relationship status	Patient & partner			1	0, 2, 4, 6
Psychiatric treatment history	Patient & partner	Question (PhenX tier 1)	Collins et al. ⁷⁵	1	0
Baseline of outcomes	Patient & partner	See rows above	Collins et al. ⁷⁵	11	0
Concurrent Tx services received	Patient	TSR	McLellan et al. ⁸⁶	6	0, 2, 4, 6
Addiction severity	Patient	DSM-5	APA ⁸⁷	11	0, 2, 4, 6
Addiction treatment level (e.g. IOP)	Patient	Administrative records	Collins et al. ⁷⁵	11	0, 2, 4, 6

Items were selected based on the conceptual model (Figure 1). When possible, we will use questions from PhenX toolkit on SUD so that results are comparable to those in other studies.⁸⁸ The survey will have 134 questions for partners and 130 for patients. Using the survey in this pilot will help us determine which items can be eliminated or altered to reduce participant burden while obtaining the data necessary to analyze our conceptual model. All measures have been validated in the empirical studies referenced above.

7.0 STUDY PARAMETERS

40 dyads will be recruited, 6 of whom will participate in development and initial testing of PartnerCHESS and the survey instruments. The remaining 34 dyads will be randomized on a 1:1 ratio to either A-CHESS + TAU or PartnerCHESS + TAU. Subjects will be stratified by gender and have access to A-CHESS or PartnerCHESS for 6 months.

Patients will have access to A-CHESS and Patients/Partners will have access to Partner CHESS for the 6 months of the study. They will be allowed to keep the phone, so that they could continue to use those interventions if they had other ways to access the two systems. Partners in the A-CHESS group will not have access to either app.

8.0 STATISTICAL CONSIDERATIONS

Outcomes. *Primary outcomes* will be measured by the Time Line Follow Back over the last 60 days.⁷⁵ Risky drinking will be >4 drinks for men and >3 drinks for women in 2 hours, the same cutoffs used in our A-CHESS RCT. These questions are also contained in the PhenX tool kit.⁸⁸ *Secondary outcomes* are treatment retention (number of weeks from first to last treatment session) using SSTAR data; negative affect (measured by PANAS⁶⁰); and sleep quality. *Exploratory outcomes* are days of other drug use and health service use per McCollister and French⁷⁷; partner risky drinking days; abuse; and satisfaction with technology, assessed with Technology Acceptance Model⁸⁰ data on ease of use, safety, acceptability, attitude toward, behavioral intention, and perceived usage.

Mediators and moderators. *Mediators* come from prior A-CHESS studies so we have comparable measures of them. Including partner mediators is new. *Moderators* are gender and use of the technologies.

Demographics and other covariates. Addiction severity will be identified by the DSM-5 categories *moderate* or *severe* based on number of symptoms present.⁸⁷ We will use an adaptation of the Treatment Services Review to track concurrent treatments that patients and/or partners are receiving.

Data analysis plan. The analysis will: (1) determine if there is a significant difference between study arms over the 6-month pilot test, and (2) explore the conceptual model (Figure 1)—i.e., the relationships between the primary and secondary outcomes and patient and partner mediators, moderators, the 2 study arms, and covariates. We will report descriptive statistics for all demographic and clinical variables in both arms to ensure that randomization produced demographically and clinically comparable groups; if not, variables with significant differences will be included as covariates in a sensitivity analysis. Analysis of the impact of PartnerCHESS+TAU vs. A-CHESS+TAU will focus on outcomes over time computed from data at pretest, 2, 4, and 6 months, with separate models for the primary outcomes and each secondary outcome. Linear mixed effects models—which account for dependence among successive observations on the same patient and incomplete data—will analyze outcomes longitudinally and at each time point. Initial intercepts will be modeled as random variables to provide variance and covariance estimates of intervention effects at each time point and across and between patients. A generalized linear mixed effects model, based on a multiple regression, will be used for the continuous outcome of risky drinking days.⁸⁹ We will conduct specific treatment time contrasts both between and within groups to test time-based effects. Sensitivity analyses (with and without covariate adjustment) will determine the robustness of covariate-related error control.

Modeling mediation and moderation. For both patients and partners, we will test the effect of the interventions on potential mediators (competence, intrinsic motivation, and relatedness) on primary and secondary outcomes, using Barron and Kenny's⁹⁰ steps: Step 1, the outcomes (e.g., risky drinking days) will be regressed on the interventions (arm 1 vs. arm 2); Step 2, mediators will be regressed on the interventions; Step 3, the intervention variable and mediator variables will be regressed on the outcomes.

Mediator effects are statistically significant if: (a) the beta-weight coefficients in Steps 1 and 2 differ significantly from zero, (b) the Step 3 beta-weight coefficient of the mediators is statistically significant, and, (c) the difference between the beta-weight coefficients of the intervention variable in Steps 1 and 3 is statistically greater than zero. We will test whether patient and partner gender moderates the effect of intervention on outcomes. We will derive interaction terms for the predictor variables, incorporating them into the regression model, and determine whether those terms significantly contribute to the outcome predictions that exist independent of other significant contributors. We will examine moderated mediation because the process may be more complex than can be rendered by treating the factors independently (e.g., a mediator may be stronger for women than men or vice versa). We will develop a moderated mediation structure to determine whether the results are best described by meaningful higher-order interaction terms based on mediator-moderator combinations.

Power. We understand that estimating effect size from pilots can lead to bad estimates. A paper by Leon, Davis, and Kraemer² points out that a pilot study can evaluate the. It informs feasibility and identifies modifications needed before a larger hypothesis-testing study. But (they argue) a pilot study does not provide meaningful effect size estimates for planning subsequent studies because of the imprecision inherent small samples. Rather, a hypothesis-testing study should be designed to detect the smallest difference that is generally agreed to be clinically meaningful. Several studies (e.g. Walters et al.)³ suggest that an effect size of $d=.35$

is considered clinically meaningful. So we will use $d=.35$ at a power of .85 to determine sample size needed for the large study.

This particular pilot is not powered to detect any effect on outcomes. Once the R34 analyses are complete, we will develop the R01 proposal based on the previous work mentioned above but also considering what we learn about the feasibility of recruitment, randomization, retention, assessment procedures, and new methods mentioned above.

Missing data. In previous RCTs, we completed about 85% of surveys through 12 months and kept missing data on core survey items to about 2%. We expect these rates in this study. In addiction treatment, data are not likely to be missing at random (i.e., the probability that data are missing relates to what the data would have been had they been observed). For example, a patient may not want to disclose some information in surveys. Because this may lead to biased parameter estimates, we will identify missing data patterns and use pattern-mixture modeling to test the sensitivity of our analysis to missing data assumptions⁹¹⁻⁹⁴ and conduct other sensitivity analyses after imputing missing data with a range of plausible values based on assumptions for the missing data (e.g., best-case, worst-case; with and without multiple imputation).⁹⁵⁻⁹⁷

Intention-to-treat and subject noncompliance. Standard intention-to-treat (ITT) estimates the average treatment effect by comparing outcomes based on assignment of the treatment, but ignoring use of the treatment. Because ITT effect estimates do not represent treatment efficacy under noncompliance (e.g., a patient is randomized to PartnerCHESS but does not use the system), we will estimate noncompliance by also estimating treatment effects only for compliers using As-treated, Per-Protocol⁹⁸ and CACE.⁹⁹

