This project will develop and pilot test a new smartphone-based system for AUD patients, their partners, and clinicians called PartnerCHESS. PartnerCHESS will integrate key features of ABCT and A-CHESS. The project has three specific aims:

1. Integrate A-CHESS with key features of ABCT to create PartnerCHESS to serve patients, partners, and clinicians.
2. Conduct a pilot test (a small randomized clinical trial) of PartnerCHESS to estimate effect size and refine the protocol, procedures, recruitment strategy, measurements, and operations we would use in a large RCT.
- 3a. Decide whether to pursue an R01 application, and if so, 3b. plan for the R01.

The project would engage 6 couples to help design PartnerCHESS, test its usability and give feedback on its utility. Once ready, the system would be tested by 34 other couples randomized to receive either PartnerCHESS + treatment as usual (TAU) or A-CHESS + TAU for a 6-month trial. We will collect survey data at baseline, 2, 4, and 6 months and analyze it to see if a large clinical trial holds promise and, if so, produce an application to support a full-scale trial based on the technology developed and the research procedures employed in the pilot test.

The study is important to public health because of the scope of the alcohol abuse and the potential of technology to improve the lives of both patients and partners. If successful, such technology could greatly broaden the reach and impact of AUD treatment in general and couples therapy in particular.

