3.0 ELIGIBILITY

Patients and Partners: A total of 40 dyads will be recruited from the community and outpatient treatment programs in Fall River, MA (Stanley Street Treatment and Resources – SSTAR) and Madison, WI (UW Behavioral Health & Recovery).

Patients and partners must:

- Must be 18 or older
- Not have a mental or physical condition that limits smartphone use

- Not report fear of being involved in PartnerCHESS or fear that their partner would hurt them physically or emotionally for being involved in PartnerCHESS
- Not have a history of schizophrenia

Patients:

- Must have a DSM-5 diagnosis of alcohol use disorder or meet NIAAA guidelines for risky drinking.
- Have had at least one alcoholic drink in the last 3 months

Partners:

- Must be a spouse, or in a 6-month or longer committed romantic relationship
- Willing to participate in the study

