4.0 REGISTRATION PROCEDURES

Patient Recruitment and Consent

Patient recruitment will be the same for both groups of participants, the 6 dyads for the initial development phase and the 34 dyads for the 6-month pilot test. The consent process will be the same although the consent form itself will be different between the two groups.

Community Recruitment: Recruitment targeting the general community in Fall River, MA and Madison, WI will be done by newspaper/Craigslist ads, flyers, and internal staff/faculty emails.

Outpatient Treatment Recruitment: SSTAR and UW Behavioral Health & Recovery staff will use medical records and client intake forms to identify and prescreen patients based on the eligibility criteria outlined in section 3.0.

After potentially eligible subjects are identified (via a phone call from the patient/partner regarding one of the community recruitment strategies or outpatient treatment staff), the research staff will explain the study and its benefits and risks via the phone. If the patient/partner is interested and believes their partner would be willing to learn more, research staff will screen the patient/partner for eligibility and discuss the options for talking with their partner - 1) if available, talk to the patient/partner on the phone directly following screening of the first member of the dyad, 2) provide research staff phone number for patient/partner to call when convenient, or 3) mail/email/text the Opt-in Letter (Partner Letter) which they can review and return if interested giving research staff permission to call and convenient times. Once the research staff has talked with both the patient and partner and they are eligible and interested, the consent forms and study information sheets will be mailed, emailed, or texted, whichever method the participants prefer. Staff will also mail the baseline surveys and a set of calendars as part of the survey instrument that will be administered on their first study call. At the first study call staff will go over the consent forms in detail, verbal informed consent will be documented, baseline surveys will be conducted, participants will be randomized, and

an app training call will be scheduled. Staff will then mail the study phones so they arrive prior to the training call, at which time they will go over the different services the app offers.

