Data collection. The 34 dyads will use the technologies for 6 months. Daily, PartnerCHESS will track triggers, relationship satisfaction, substance use, and cravings. Weekly, it will track the homework couples are doing; every 2 months, surveys will track the skills couples are using. UW staff will conduct surveys over the phone. While partners of A-CHESS patients will not receive software, they will be surveyed. Each patient and partner in the PartnerCHESS group and patients in the A-CHESS group will receive \$20 for each completed survey. Partners in the A-CHESS group will receive \$50 for each completed survey. In addition, if patients and partners in the PartnerCHESS group and patients only in the A-CHESS group have a smartphone, they will be paid \$50 per month towards their phone service in addition to the payments for completing surveys. If patients and partners in the PartnerCHESS group and patients in the A-CHESS group do not have a smartphone, they will be given one with paid service for 6

months. As appropriate, participants will provide feedback about what is helpful in the system and changes they would make. SSTAR will provide retention data.

App use data will be automatically collected by the technologies by placing “cookies” on smartphones (with participants’ consent) when randomization takes place. Data are stored on a central server, maintained by UW-Madison Division of Information Technology (DoIT), for protection in case of phone loss. Remaining data will come from patient surveys and be entered into REDCap, a secure, web-based application designed to support data management for research. After baseline data collection, surveys will omit stable data. UW staff will periodically call participants to promote system use and response to assessments. The timing of surveys will be based on enrollment date. The payment we selected is consistent with what we have used successfully in earlier studies.

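### The 60-day drinking calendar has no rule for missed, early or late surveys, so some follow-up days go uncollected or fall on the wrong side of randomisation

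*Combined protocol and SAP*

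**What the plan says.** Section 8.0 (Outcomes) states that the primary outcomes "will be measured by the Time Line Follow Back over the last 60 days". Table 2 in section 6.0 gives the source of both as "TLFB every 60 days (PhenX" toolkit), at months 0, 2, 4 and 6. The summary at the front of the protocol gives the same schedule: "We will collect survey data at baseline, 2, 4, and 6 months".

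On timing, section 5.0 (Data collection) says "The timing of surveys will be based on enrollment date". Section 4.0 puts the baseline survey and the allocation on the first study call, in that order: "baseline surveys will be conducted, participants will be randomized". Enrolment and randomisation can therefore be taken as the same day.

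On completeness, section 8.0 (Missing data) reports that in previous trials "we completed about 85% of surveys through 12 months" and expects the same rate here. It also expects missingness to depend on the unobserved values. Its remedies are pattern-mixture models and imputation under a range of assumptions, on top of the mixed models in the data analysis plan.

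The documents give no tolerance around the call dates, no instruction for a calendar after a missed survey, no cut-off at randomisation, and no conversion of day counts to days covered.

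**The concern.** A Time Line Follow Back is a dated calendar, so in principle each day can be placed before or after randomisation, and a missed stretch can be filled in at the next contact. A look-back of 60 days from whenever the call takes place gives up both advantages.

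- **Missed survey.** The next call covers only its own last 60 days. The skipped 60 days stay unobserved although the patient is on the phone completing a calendar.
- **Month-2 call off schedule.** An early call brings pre-randomisation drinking into a follow-up outcome. A late call misses the first days after randomisation, and an on-time month-4 call then counts some days twice.
- **Month-4 or month-6 call off schedule.** Windows overlap or leave gaps between them.

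At stake is the content of both primary outcomes. The plan itself expects missed surveys to be related to drinking, and with about 15 dyads per arm a pattern-mixture model has few patients in each pattern. Days that can be collected are better than days that must be modelled.

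**Working it through.** **The plan's own figure.** Section 5.0 expects about 10% dropout and about 15 dyads per arm to complete. 34 × (1 − 0.10) / 2 = 15.3, which agrees.

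**Inputs.** 34 randomised dyads (section 7.0: "The remaining 34 dyads will be randomized on a 1:1 ratio"); three follow-up windows of 60 days (section 8.0 and Table 2); 85% completion (section 8.0); 10% dropout (section 5.0). The pattern of misses and the size of call drift are not stated and are assumed below.

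**1. Calls exactly on schedule.** Three windows cover 3 × 60 = 180 of about 183 days, so about 1 day per two months is uncovered. That is negligible.

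**2. Missed surveys, fixed 60-day look-back.** There are 34 × 3 = 102 windows, or 102 × 60 = 6,120 person-days. At 15% missed, 102 × 0.15 = 15.3 windows (918 person-days) are unobserved. If misses are independent, 34 × (1 − 0.85³) = 13.1 patients have at least one gap.

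**3. Missed surveys, reaching back to the last completed survey.** A window stays unobserved only if that survey and every later one are missed.

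*Independent misses* (q = 0.15):
- Month 2: q³ = 0.3%. Month 4: q² = 2.3%. Month 6: q = 15%.
- Windows lost: 34 × (0.0034 + 0.0225 + 0.15) = 6.0 (5.9%), or 359 person-days.

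*Mixed case*: permanent dropout accumulates to 3.33%, 6.67% and 10% at months 2, 4 and 6, total missing is 15% at each survey, and the remaining misses are intermittent.
- Month 6: 15%.
- Month 4: 6.67% already dropped out. Another 8.33% miss intermittently; of these a share 0.0357 + 0.9643 × 0.0556 = 0.0893 also miss month 6. Total 6.67% + 8.33% × 0.0893 = 7.4%.
- Month 2: 3.33% already dropped out. Another 11.67% miss intermittently; of these a share 0.0345 + 0.9655 × 0.0893 × 0.0893 = 0.0422 never return. Total 3.33% + 11.67% × 0.0422 = 3.8%.
- Windows lost: 34 × (0.0383 + 0.0741 + 0.15) = 8.9 (8.7%).

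*All misses permanent*: nothing is recovered, and 15.3 windows stay lost.

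| Completion | Lost, fixed 60 days | Lost, reaching back (independent misses) |
|---|---|---|
| 80% (assumed) | 20.4 | 8.4 |
| 85% (plan) | 15.3 | 6.0 |
| 90% (assumed) | 10.2 | 3.8 |

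**4. Call timing at month 2.** With the call d days after randomisation, pre-randomisation days counted = max(0, 60 − d), and early post-randomisation days unobserved = max(0, d − 60). The values of d are illustrations.
- d = 53: 7 days, 7/60 = 12% of the window. d = 46: 14 days, 23%.
- d = 67: the first 7 days are unobserved, and a month-4 call at day 120 counts 7 days a second time. d = 74: the first 14 days are unobserved.

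Only the month-2 call can cross randomisation. With a date-anchored calendar both month-2 quantities are zero.

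**The case against.** The strongest reply is that silence is not a prohibition. Sixty days is simply the interval between scheduled surveys, nothing tells the caller to stop at 60 days after a missed survey, and the calendar instrument is not among the documents. That stands as a limit: a reader might infer that missed days are irrecoverable by design, and the documents do not say so. But nothing requires or standardises a longer look-back either, and staff who follow the text would stop at 60 days.

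A reader might also infer that reaching back would cure informative missingness. It would not. Month 6 stays at 15% missing, permanent dropouts are not recovered, and the plan's own example, a patient unwilling to disclose, is untouched by a longer calendar. The planned sensitivity analyses are still needed.

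A third inference is that drift would bias the comparison. Both arms follow the same schedule and the documents give no reason for timing to differ by arm, so noise or dilution is the likelier effect.

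A fourth is that a 60-day baseline conflicts with the entry criterion "Have had at least one alcoholic drink in the last 3 months". It does not: an entry criterion and an outcome window serve different purposes, and an abstinent 60-day baseline is a legitimate value.

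The daily substance-use tracking that section 5.0 describes for PartnerCHESS is no substitute. It is not named as a source for the primary outcomes, and using it to fill gaps could treat the arms unequally.

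Finally, longer recall is less accurate and mixes recall lengths. That cost is real.

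**Conclusion.** The point holds as a modest, inexpensive improvement to how both primary outcomes are collected. As written, about 15.3 of 102 follow-up windows would be unobserved at 85% completion. Reaching back would reduce this to about 6.0 with independent misses or about 8.9 in the mixed case, with no gain if every miss is permanent. Since the plan expects about 10% dropout but about 15% missed surveys, some misses are plausibly intermittent, though the documents do not give the split. The gain falls at months 2 and 4 only.

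The timing effect is a matter of counting days, but its size depends on a drift that the plan does not state.

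Section 8.0 says the pilot is not powered for outcomes, which limits the consequence here. It still matters because Specific Aim 2 includes refining the measurements for the larger trial, and an unanchored calendar would carry over into it.

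**What to change.** In the survey script and section 8.0:

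1. At each follow-up, start the calendar on the day after the last day covered by a completed survey, never before randomisation, and run it to the day before the call.
2. Assign each day to a fixed period counted from randomisation (for example days 1–60, 61–120 and 121–180), whichever call supplied it.
3. Analyse risky and abstinent days per days covered in the period.
4. Flag days recalled from more than 60 days back and repeat the analysis without them.
5. Keep the planned missing-data sensitivity analyses.

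The cost is script and SAP wording, plus a longer call and less accurate recall for the patients who missed a survey. Step 4 shows whether the recall problem matters. The 60-day baseline needs no change.

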Regarding imminent harm to self or others, a specific safety protocol will be in place at the treatment site. If participants experience any crises during the study period, they will be instructed to contact their clinician if currently in treatment or the site researcher if no clinician is available during working hours. If the risk to self or another is imminent, we will collaborate with staff to ensure that clinical staff evaluate the need for emergency services and triage the participant to receive appropriate services. If participants have crises after hours, they will be instructed to call 911 for imminent risk or go to a local emergency room crisis center. All participants will be provided with a listing of crisis hotline numbers and community resources that participants may access 24/7, such as the National Drug Abuse [contact]), the National Domestic Violence [contact]), or a Crisis Hotline for any crisis [contact]). For patients in the A-CHESS condition and patients and partners in the Partner-CHESS condition, these numbers will be set up in their safety plan and stored for use with the "panic button" service, which the participant will be trained to use as part of the

intervention.

Lost or Stolen Smartphone: Participants will be informed that if the phone is in the hands of another person there is the potential that someone might see the information they stored on the phone (personal contacts, text messages). Participants are advised to make their phone password protected to reduce the risk of someone being able to see their information if the phone is lost or stolen.

Phone service for the study phone is terminated at the end of the 6 month study period: The study coordinator will explain this prior to informed consent and will inform the participants well in advance of the service ending so they have time to get their own service if they wish.

To help us further protect participant privacy, we will obtain a Certificate of Confidentiality from the National Institutes of Health.

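### Treatment retention is undefined for patients with no treatment sessions, has no clearly named source for UW-clinic patients, and is not anchored at randomisation

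*Combined protocol and SAP*

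**What the plan says.** Three places in the combined protocol and SAP describe the source of the outcome.

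- Section 8.0, Outcomes: "treatment retention (number of weeks from first to last treatment session) using SSTAR data".
- Section 5.0, Data collection: "SSTAR will provide retention data".
- Section 6.0, Table 2: the source is "Clinic records", with no clinic named, at months 0, 2, 4 and 6.

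The population is wider than SSTAR. Section 3.0 says "A total of 40 dyads will be recruited from the community and outpatient treatment programs in Fall River, MA" and goes on to name SSTAR and UW Behavioral Health & Recovery in Madison. Section 4.0 describes two routes. For the community: "Recruitment targeting the general community in Fall River, MA and Madison, WI will be done by newspaper/Craigslist ads, flyers, and internal staff/faculty emails". For the clinics: "SSTAR and UW Behavioral Health & Recovery staff will use medical records and client intake forms to identify and prescreen patients".

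The clinical criterion for patients is "Must have a DSM-5 diagnosis of alcohol use disorder or meet NIAAA guidelines for risky drinking", together with a drink in the past three months. No criterion concerns being in treatment or when treatment began. The crisis instructions in section 5.0 allow for participants outside care, who are told to "contact their clinician if currently in treatment or the site researcher if no clinician is available". Under section 4.0, randomisation happens at the first study call, with no link to the start of treatment.

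**The concern.** The definition would fit a trial that enrols every patient from one clinic as treatment begins. The treatment-as-usual paragraph in section 5.0 still describes SSTAR as the recruitment site, but sections 3.0 and 4.0 describe three streams. Three gaps follow.

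1. A patient with no sessions has neither a first nor a last session, and no scoring rule is given.
2. A UW-clinic patient has sessions, but two of the three passages point to another clinic's data.
3. For a patient already in care, the count begins before assignment and includes time that neither app could influence. No end of window is stated either.

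At stake are the number of patients who contribute to this outcome, the precision of the comparison, and whether a usable measure is passed on to the larger trial. Refining measurements is a stated purpose of the pilot (section 2.0, Specific Aim 2).

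**Working it through.** **The plan's own figure.** Section 5.0 expects about 15 dyads per arm to complete. 34 / 2 × (1 − 0.10) = 15.3, so it reproduces. No sample size or power is tied to retention.

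**Who has a value under the stated rule**

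| Patient | First and last session exist? | Source named? |
|---|---|---|
| SSTAR patient | Yes | Yes, in sections 5.0 and 8.0 |
| UW-clinic patient | Yes | Only if Table 2's generic entry is read to include UW records |
| Community recruit attending SSTAR | Yes | Yes |
| Community recruit not in treatment | No | Not applicable |

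Section 8.0's missing-data methods (pattern-mixture models, imputation under a range of assumptions) suit values that exist but were not observed. They do not give meaning to a duration between sessions that never took place.

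**Precision if only SSTAR records are used.** The SSTAR share is not in the documents, so the shares below are assumptions. With n patients per arm, the 95% CI half-width for a standardised difference is t(0.975, 2n − 2) × √(2/n).

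| Assumed SSTAR share | Patients (34 × share) | n per arm, rounded | Half-width (SD) |
|---|---|---|---|
| 100% | 34 | 17 | 2.037 × 0.343 = 0.70 |
| 65% | 22.1 | 11 | 2.086 × 0.426 = 0.89 |
| 33% | 11.2 | 6 | 2.228 × 0.577 = 1.29 |
| 25% | 8.5 | 4 | 2.447 × 0.707 = 1.73 |

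These are randomised numbers. Counting completers only (10% lost), with a normal approximation, gives 15.3 per arm and 0.71 SD at 100%, and 3.8 per arm and 1.42 SD at 25%.

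**Effect of weeks before randomisation.** Let r be the SD of pre-randomisation weeks divided by the SD of on-study weeks, the two assumed independent. If the total is compared with no baseline adjustment, a true standardised effect d becomes d / √(1 + r²). Section 8.0 uses d = 0.35 for planning the later trial, so:

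- r = 0.5: 0.35 / 1.118 = 0.31
- r = 1: 0.35 / 1.414 = 0.25
- r = 2: 0.35 / 2.236 = 0.16

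The values of r are assumptions. Assignment is random, so the expected pre-randomisation total is the same in both arms. The raw difference in mean weeks is therefore unbiased, and only its variance rises.

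**The case against.** The strongest reply is that a good deal of this is already covered, and four stronger readings that a reader might draw do not hold.

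**That SSTAR is the exclusive source, so every non-SSTAR patient is missing by design.** No passage says exclusive, and Table 2's entry could include UW records. A Fall River community recruit may also attend SSTAR. For UW patients the fault is inconsistent naming; only for patients with no sessions is the value truly undefined.

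**That pre-randomisation weeks bias the comparison.** They do not, on average. Section 8.0 also plans mixed models that include the pretest value, with random intercepts and time contrasts. Time already in care is a patient-level offset present at month 0, and such a model can absorb much of it. What remains is that the plan also analyses outcomes at each time point and does not say that retention will be baseline-adjusted.

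**That an imbalance in recruitment source would pass for an arm effect.** This requires untreated patients to be scored as zero weeks. The plan contains no such rule. If those patients are simply missing, the main effect is on precision.

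**That this definition is what stops the trial from answering the retention question.** Section 8.0 says the pilot is not powered for any outcome. Even with all 34 patients the half-width is 0.70 SD, twice the planning effect of 0.35.

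It is also fair to say that the Treatment Services Review already gives a treatment measure for every patient. It does not repair the retention definition, but it makes the gap cheaper to close.

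**Conclusion.** The concern holds as a defect of definition and data source with modest consequences. The three descriptions of the source do not agree, patients with no sessions have no defined value, and the count is anchored neither at randomisation nor at the end of follow-up.

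The result is a smaller sample and lower precision for one secondary outcome of a pilot not powered for outcomes. If only SSTAR records are used, and SSTAR supplies 25% to 65% of the 34 patients, about 4 to 11 per arm contribute and the half-width is about 1.7 to 0.9 SD, against 0.7 SD with all 17. These figures rest on assumed shares. The dilution from pre-randomisation weeks rests on an assumed SD ratio and an analysis without baseline adjustment. It should be corrected mainly because the pilot's measures are meant to carry forward to the larger trial.

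**What to change.** - **Source.** Reconcile sections 5.0 and 8.0 with Table 2 so that SSTAR and UW clinic records are both named.
- **Definition.** Count weeks from randomisation to the last session within 26 weeks (6 months × 52/12). The month-0 value is then zero by construction and can be dropped.
- **Denominator.** Restrict the outcome to patients with an open treatment episode at randomisation, say how that is read from the record, and report the number by arm. Because membership is fixed at baseline, the randomised comparison is kept within the subset.
- **All patients.** Use the Treatment Services Review, already collected at months 0, 2, 4 and 6 (Table 2), to describe treatment received by arm for all 34.

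The cost is protocol wording and one record extraction from the UW clinic, which already prescreens from records. There are three downsides. The retention result will apply only to patients in treatment at randomisation, so anyone who enters treatment later is seen only through the Treatment Services Review. The signed authorisations must cover the use of UW records for outcomes. The all-patient measure is self-report.
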